Aim 3 (Exploratory): To investigate whether structural, functional, and chemical brain imaging provides evidence of the neurobiological signature for centralized pain in patients who fail to derive benefit from lumbar spine surgery. To accomplish this aim, a small subset of lumbar spine surgery patients, healthy controls, and established-FBSS patients will undergo structural, functional, and spectroscopy MRI brain imaging, as recent research has shown alterations in all three imaging paradigms can identify stereotypical features of centralized pain. *Exploratory Hypothesis 3: Lumbar spine surgery patients with increased pre-operative levels of centralized pain (measured by the 2011 Fibromyalgia Survey Criteria score) will exhibit increased neuroimaging findings (stronger neuroimaging presence of CNS pain amplification, altered brain structure, and abnormal levels of CNS neurotransmitters) compared to those with lower levels of centralized pain.*

B. Background and Significance

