Aim 3 (Exploratory): To investigate whether structural, functional, and chemical brain imaging provides evidence of the neurobiological signature for centralized pain in patients who fail to derive benefit from lumbar spine surgery. To accomplish this aim, a small subset of lumbar spine surgery patients, healthy controls, and established-FBSS patients will undergo structural, functional, and spectroscopy MRI brain imaging, as recent research has shown alterations in all three imaging paradigms can identify stereotypical features of centralized pain.

B. Study Type and Design:

Pain perception is a complex process composed of both physical and psychosocial components. Physicians from different training backgrounds often approach and view pain in varying ways. One of the major strengths of this proposal is the *diversity in the backgrounds of the research and mentor team, including anesthesiology/pain management, internal medicine and rheumatology, brain imaging, and neurosurgery*. Drs. [name] and [name] along with and other researchers at the University of Michigan are internationally recognized for their leadership in the development and refinement of research methods designed to “phenotype” individuals with chronic pain.^{53,60,82-116} Their highly rigorous and reproducible methods were originally developed and applied in the context of gaining a better

understanding of FM, but they have also used them to help identify CNS pain amplification in other chronic pain conditions.^{36,53,54,57,97,100,101,104,105,108,112,113,117-130}

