Overall Study Design. For Aims 1 and 2, a prospective, observational study will recruit 100 men and women with chronic low back pain (+/- leg pain) who are scheduled to undergo lumbar spine surgery at the University of Kansas Medical Center (KUMC). 50 will participate in phenotypic characterization and 50 will participate in phenotypic characterization and quantitative sensory testing (QST) procedures. After screening, informed consent, and enrollment into the study, all subjects will undergo an evaluation which includes a comprehensive battery of questionnaires for patient phenotyping that will assess symptoms including pain, physical function, depression, anxiety, and catastrophizing symptoms. QST parameters will only be performed on half of the cohort of lumbar spine surgery patients. Patient phenotyping and QST procedures will take place in one visit pre-operatively. At two weeks, one month, three months, & six months post-surgery, we will administer one questionnaire to determine analgesic response to surgery. This will establish longitudinally-designated post-surgical analgesic outcome groups (see Statistical Analysis section for definitions). Instead of just a three month time point that is often used in analgesic trials, a six month time point was chosen to give adequate time for recovery and response to surgery. Phenotyping and QST will also be done in a cross-sectional manner on 50 age and sex-matched healthy controls and 50 age and sex-matched patients with an established diagnosis of FBSS (established-FBSS) to compare to the longitudinally-designated post-surgical analgesic outcome groups. For Aim 3, 30 men and women with chronic low back pain (+/- leg pain) who are scheduled to have lumbar spine surgery at KUMC will undergo pre-operative functional, structural, and chemical neuroimaging studies. 15 age and sex-matched healthy controls and 15 age and sex-matched established-FBSS patients will also undergo the same neuroimaging studies to compare to the longitudinally-designated post-surgical analgesic outcome groups. Patients for Aim 3 will be recruited from both the prospective and cross-sectional cohorts enrolled for Aims 1 and 2. The goal of the studies in Aim 3 are to investigate whether pre-operative functional, structural, and chemical neuroimaging findings known to be associated with centralized pain and indicative of CNS amplification are associated with the centralized pain phenotype and possibly predictive of failure to achieve pain relief after lumbar spine surgery. We acknowledge that these studies are exploratory and may be underpowered but feel that they will at a minimum provide critical preliminary data for future studies.

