Aim 2 Analyses: To confirm that altered pain processing mechanisms consistent with centralized pain are seen in patients who have failed to respond to lumbar spine surgery. Pain thresholds, cuff algometry, CPM, and temporal summation scores will be treated as continuous measures and normality will be assessed prior to analysis. The same analyses as those conducted for Aim 1 will be used for this aim.

Aim 3 Analyses: To investigate whether structural, functional, and chemical brain imaging provides evidence of the neurobiological signature for centralized pain in patients who fail to derive benefit from lumbar spine surgery. AFNI, BrainVoyager, LCMoel, FSL, MatLab, SPM, and Freesurfer will be used for functional MRI, structural MRI, and spectroscopy MR analyses based on the analytical methods previously described by [name] and his research colleagues.^{54,58,74,76,122,131-141} **Analysis 3a:** Pre-operative neuroimaging data for lumbar spine surgery patients will be split based on median baseline 2011 FM Survey Criteria score into two groups (FM-high and FM-low). Neuroimaging findings between these two groups will be compared and we hypothesize that lumbar spine surgery patients with higher preoperative 2011 FM Survey Criteria scores will have (1) *more hyperalgesia and decreased pain inhibition on QST and functional magnetic resonance imaging (fMRI)*, (2) *characteristic functional connectivity changes on fMRI (e.g., decreased functional connectivity to descending anti-nociceptive analgesic brain networks and increased connectivity to pro-nociceptive regions)*, (3) *increased CNS levels of glutamate in pro-nociceptive regions on proton spectroscopy*, and (4) *increases in S1/M1 gray matter volume*. **Analysis 3b:** We will perform whole brain analyses as per analysis 3a for all modalities with no *a priori* hypotheses to investigate the relationships between baseline imaging findings and post-surgical analgesic outcome status (AOC-success and AOC-failure) at six months.

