Magnetic Resonance Imaging: In addition to QST, patients enrolled in Aim 3 studies will also undergo four different neuroimaging procedures (all in one visit) to identify brain regions and associated neurotransmitters operative in pain processing and modulation: 1) *Functional connectivity MRI* (fcMRI) will be performed at rest, 2) *Proton magnetic resonance spectroscopy* (¹H-MRS) of the insula (anterior and posterior) as well as the anterior cingulate cortex (ACC) assessing combined glutamate and glutamine (Glx), 3) *Evoked pain fMRI* will be used with evoked thumb nail pressure pain to avoid affected body sites as well as tonic cuff pressure (at Pain 40), and 4) *Voxel based morphometry to assess gray matter volume in the primary somatosensory cortex (S1) and motor (M1) cortex*. The specific neuroimaging methods have

been employed heavily by [name] research group and are described in detail in their published research.^{54,58,74,76,122,131-141} We will utilize these exact imaging protocols and adapt them for use in the Siemens Skyra 3T scanner at the KUMC Hoglund Brain Imaging Center. These different procedures investigate varying aspects of the brain's involvement in pain processing and modulation that will complement the QST methods by further providing a comprehensive picture of the neurobiological presence of pain centralization. Comprehensive training and familiarization procedures will be completed prior to MRI to reduce anxiety. Participants will be instructed that the neuroimaging can be stopped at any time if a procedure becomes unbearable. As for QST, all procedures have been evaluated for safety and are well tolerated by chronic pain patients and controls. Neuroimaging will require approximately 2 hours to complete.

All study procedures are solely for research purposes and none are part of usual standard therapy. No study procedures will be billable to insurance companies.

Timeline: **See last page.**

1. Risk/benefit assessment:

Physical risks:

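### Aim 3 is titled for patients who fail surgery, but every directional imaging prediction concerns baseline FM score; outcome enters only through Analysis 3b, a whole-brain search with no hypothesis, worded so that spectroscopy cannot follow it

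*Combined protocol and SAP*

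**What the plan says.** Section II.A and the Aim 3 Analyses in II.C give the aim as asking whether imaging "provides evidence of the neurobiological signature for centralized pain in patients who fail to derive benefit from lumbar spine surgery". The Overall Study Design in II.B words the goal in two parts: whether pre-operative findings "are associated with the centralized pain phenotype and possibly predictive of failure to achieve pain relief after lumbar spine surgery". It adds: "We acknowledge that these studies are exploratory and may be underpowered".

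Exploratory Hypothesis 3, in the opening statement of aims, is about FM score alone: "Lumbar spine surgery patients with increased pre-operative levels of centralized pain (measured by the 2011 Fibromyalgia Survey Criteria score) will exhibit increased neuroimaging findings". Analysis 3a follows it: "Pre-operative neuroimaging data for lumbar spine surgery patients will be split based on median baseline 2011 FM Survey Criteria score into two groups". Four directional predictions are attached to that split: hyperalgesia and reduced inhibition, connectivity, glutamate, and S1/M1 gray matter volume.

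Analysis 3b brings in the six-month outcome (AOC-success or AOC-failure): "We will perform whole brain analyses as per analysis 3a for all modalities", with no prior "hypotheses to investigate the relationships between baseline imaging findings and post-surgical analgesic outcome status".

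The Magnetic Resonance Imaging part of II.E places proton spectroscopy in voxels "of the insula (anterior and posterior) as well as the anterior cingulate cortex (ACC". The sample size text in II.C gives 30 surgery patients for Aim 3 and no power calculation.

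**The concern.** The contrast that carries the predictions is not the one that the aim's title names. Analysis 3a uses two baseline quantities, FM score and imaging. It can show that they go together before surgery, but it says nothing directly about who later fails. The contrast that does use failure names no measure, region or direction.

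At stake is what can be reported. A clear 3a result could be written up under an aim titled for surgical failure although the imaging measures have no relation to failure. The future studies that II.B wants to inform would then receive no focused estimate of the imaging difference between failures and successes.

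**Working it through.** **Plan's own figures.** No power is stated for Aim 3. The only stated figures are for Aim 1 (50 vs 50, two-sided 0.05). With p̄ the mean of the two proportions, z = [|p2 − p1|√n − 1.96√(2p̄(1 − p̄))] / √(p1(1 − p1) + p2(1 − p2)). For 0.10 vs 0.50: (2.828 − 1.270)/0.583 = 2.67, power 0.996 (plan: 0.99). For 0.15 vs 0.45 and 0.17 vs 0.43 the results are 0.918 and 0.820 (plan: 92% and 82%). They reproduce, but they do not bear on imaging.

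**Which analysis contains what**

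| Element | Contrast | Outcome used? | Direction given? |
|---|---|---|---|
| Aim 3 title | patients who fail surgery | yes | – |
| Exploratory Hypothesis 3 | higher vs lower FM score | no | yes |
| Analysis 3a | FM-high vs FM-low | no | yes, four predictions |
| Analysis 3b | AOC-failure vs AOC-success | yes | no |

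**Can 3a be positive with no link to failure?** Inputs: 30 patients, hence 15 vs 15 after a median split; two-sided 0.05 (stated for Aim 1, assumed here); one imaging measure and a t-test (assumed). The noncentrality is λ = d√(n1n2/(n1 + n2)) with 28 degrees of freedom and critical value 2.048.

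- d = 0.8: λ = 0.8 × √(225/30) = 2.19, power 56%.
- d = 1.0: λ = 2.74, power 75%.

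In a simulation (40,000 runs) failure risk was set at 30% in both FM groups, so imaging had no relation to failure. 3a was significant in 56% and 75% of runs, and the outcome contrast in about 5%, its false-positive rate. The 3a result does not depend on the failure rate, because failure is not an input. If FM score drives both imaging and failure (failure 0.10 vs 0.50), imaging is indirectly linked to failure; the outcome contrast is then significant in 14% and 18% of runs.

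**What a pre-specified outcome test could detect.** The number of failures among 30 is not stated. The mean of the plan's 0.10 and 0.50 gives 30%, or 9 vs 21; I show 3 to 12 failures. The 0.0125 level is 0.05/4, one test per prediction. The 0.001 level is an assumed single-voxel threshold, since the plan states none. For 9 vs 21, √(189/30) = 2.51.

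| Failures vs successes | Detectable d (80% power, 0.05) | Power at 0.0125, d = 0.8 / 1.0 / 1.2 | Power at 0.001, d = 0.8 / 1.0 / 1.2 |
|---|---|---|---|
| 3 vs 27 | 1.77 | 10% / 17% / 26% | 2% / 4% / 7% |
| 6 vs 24 | 1.32 | 20% / 33% / 49% | 4% / 10% / 18% |
| 9 vs 21 | 1.16 | 27% / 45% / 64% | 7% / 16% / 29% |
| 12 vs 18 | 1.08 | 32% / 51% / 71% | 9% / 20% / 35% |

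The difference between the last two columns runs from about 9 points (3 failures, d = 0.8) to about 35 (12 failures, d = 1.2). With 8 to 10 tests instead of four, power at d = 1.0 and 9 vs 21 falls from 45% to 32-35%.

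**Spectroscopy.** 3b calls for whole-brain analysis of every modality, while II.E acquires spectra only in insula and anterior cingulate voxels. The two cannot both hold as worded. This needs no assumption.

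**The case against.** The strongest reply is that the plan is candid and complete at its own level. II.B gives Aim 3 two goals, and each has an analysis: 3a for the phenotype, 3b for failure. Hypothesis 3 is worded on FM score, exactly as 3a tests it. The aim is labelled exploratory and possibly underpowered, and V.B says that the study has no success or failure. This stands. A reader might infer that Aim 3 has no outcome analysis, or that a positive 3a lets the sponsor declare the aim supported. The documents support neither: 3b is an outcome analysis, and no rule for declaring support exists.

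A second reply is that 3b for spectroscopy can only mean comparing the insula and cingulate values by outcome, so that test is implied. That is fair. What is missing is accurate wording, a direction and priority.

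A third reply concerns the remedy. A reader might take 3a to have defined and extracted the region measures already. It has not. Within 3a only S1/M1 is a named region; glutamate is placed in unspecified pro-nociceptive regions, with the sites given only in II.E; and connectivity is given by example, without seeds or targets. 3b's reference back to 3a even suggests that 3a may itself be whole-brain. This stands and adds to the cost of the fix.

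**Conclusion.** The point holds as a gap in pre-specification. All directional predictions concern baseline FM score. The failure goal rests on an undirected whole-brain search in 30 patients, whose wording does not fit spectroscopy. A positive 3a is compatible with no imaging-failure link, with 56-75% probability per test at 0.8-1.0 SD under the stated assumptions. Combined with an Aim 1 association between FM score and failure, it would be only indirect evidence.

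A reader might go further and infer that the whole-brain search must miss even large effects, or that named tests gain a fixed 30-35 points of power. Neither follows. The gain is about 9-35 points over 3-12 failures and d = 0.8-1.2, with four tests and an assumed voxel threshold of 0.001, and it shrinks with more tests. A search over many voxels or clusters also does not have the power of a single voxel, and the plan gives no threshold. The case for change rests on the missing outcome comparisons, and the power gain should not be quoted as a single figure. For an exploratory aim this is a worthwhile, inexpensive improvement; it does not invalidate the plan.

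**What to change.** In Analysis 3b, name a short list of comparisons between AOC-failure and AOC-success on measures already acquired: Glx in insula and anterior cingulate, S1/M1 gray matter volume, evoked-pain response, and a few connectivity contrasts with seeds and targets fixed beforehand. Carry over the directions predicted in 3a, correct for the number of tests actually listed, and report each estimate with its confidence interval.

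Keep the whole-brain functional, connectivity and morphometry analyses as secondary. Drop the whole-brain wording for spectroscopy. State that 3a supports only a link between FM score and imaging, and that any Aim 3 statement about surgical failure rests on 3b.

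Cost: no extra scans, visits or patients, and outcome status is already collected. The real work is choosing regions, seeds and summary measures before outcomes are examined. The listed tests remain modestly powered (27-64% at 0.0125 for d = 0.8-1.2 with 9 vs 21), so the intervals are the main product for planning later studies.

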(FM) Survey⁶⁶ is hypothesized to be a surrogate measure of the degree of centralized pain. Wolfe coined the term “fibromyalgia-ness” (FMness) to describe the phenomenon that where an individual lies on this FM continuum markedly influences how much pain they will experience in response to peripheral nociceptive damage or an inflammatory process.⁶⁷ Recent well-powered, prospective studies (described in detail below) have shown that increasing FMness strongly predicts poor analgesic outcomes *and* decreased responsiveness to opioids after surgery meant to improve pain.^{11,12,14}

Although there are no definitive laboratory tests or single biomarker of pain centralization, multiple constructs can be used to infer its presence. Neuroimaging has been shown to corroborate QST findings of diffuse hyperalgesia and altered endogenous pain modulation in centralized pain states.^{35,54,68-70} Recent neuroimaging studies provide additional insight into the underlying CNS changes in centralized pain, and demonstrate notable structural, chemical, and functional changes in pain-related brain areas. Structural alterations in gray matter are seen in pain processing regions such as the thalamus, insula, cingulate, and somatosensory cortices.⁷¹ Neurochemical changes include increased levels of excitatory neurotransmitters (e.g., glutamate) and decreased levels of inhibitory neurotransmitters (e.g., γ -aminobutyric acid (GABA)).⁷² Finally, increased resting brain network connectivity to pro-nociceptive brain areas and reduced connectivity to anti-nociceptive brain areas are also commonly present.⁷³⁻⁷⁶ Together, these QST and neuroimaging findings are believed to represent the neurobiologic signature for centralized pain.

*Surgical procedures and peripherally-directed interventions are postulated to be less effective for individuals with centralized pain as they may fail to address the underlying CNS amplification.*⁷⁷⁻⁸⁰

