Sample size for Study Procedures in Aims 1 and 2: We anticipate screening approximately 60 pre-operative lumbar spine surgery patients per year for possible enrollment into the study. Assuming a 50-60% recruitment rate, we estimate approximately 30-35 lumbar spine surgery patients enrolled per year during Years 1-4 of the award. This leads to an estimated total sample size of 100 lumbar spine surgery patients. We will also aim to recruit and enroll equal distributions of established-FBSS patients (n=50) and healthy controls (n=50). For the assumed effect size (population of 0.10 vs 0.50) and sample sizes (50 and 50 based on 2011 FM Survey Criteria score median split) and $\alpha=.05$ (two-sided) the power is 0.99. Several different assumptions were also explored. For example, if the assumed effect size is (population of 0.15 vs 0.45) or (population of 0.17 vs 0.43), then the respective power calculations are 92% and 82%, both which are adequate for significance purposes (e.g., >80%). The larger sample size will also be important for exploring multivariate models and potential subgroup analyses. The inclusion of healthy controls and established-FBSS patients will ensure adequate matching of gender and age to the patient cohorts for analyses.

Sample size for Study Procedures in Aim 3: We aim to recruit 30 lumbar spine surgery patients, 15 healthy controls, and 15 established-FBSS patients out of the total cohort to participate in the

neuroimaging study procedures. As this study is powered for the primary hypothesis in Aim 1, issues of power are of less concern for these investigatory neuroimaging studies.

D. Subject Criteria (See Vulnerable Populations appendix, if applicable):

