Quantitative Sensory Testing (QST): Pain testing for a variety of parameters will be performed using various pain testing devices as described below. QST requires significant training of personnel, manuals of operations and procedures, scripting, and other techniques to get good reproducible results. Participants will be familiarized with the procedures and equipment before testing. Half of the patients (n=50) patients undergoing lumbar spine surgery will complete this testing pre-operatively. Healthy controls and patients with established FBSS will only perform this testing once. Patients who participate in Aim 3 studies will also have a portion of the QST listed below as part of their MRI experimental protocol (see below).

- *Generalized Pressure Pain Sensitivity.* Pressure pain threshold (PPT) at the mid-trapezius (an unaffected site in all cohorts) will serve as the primary measure of generalized pain sensitivity in all participants (*trap-PPT*). Increased pain sensitivity at remote or unaffected body areas is strongly suggestive of central pain mechanisms and occurs in many chronic pain conditions. Here, PPT will be measured bilaterally using a digital algometer with a 1-cm² rubber probe (Somedic, Hörby, Sweden). Pressure will be manually increased at a rate of 30-50 kPa/s (1000 kPa max). Participants will press a response button to indicate their first sensation of pain. Pressure intensity at the time of button press is recorded as the PPT. Measurements will be conducted 3x/side (20-s intervals) with means used for analysis. Pressure-evoked pain at the thumbnail will serve as a secondary measure of generalized pain sensitivity, using the Multimodal Automated Sensory Testing (MAST) System, a computerized QST device developed at the University of Michigan, and currently being employed in several clinical trials, including the NIH MAPP network.

My mentors have extensive experience using thumbnail pressure as an evoked pain stimulus. The MAST system will deliver an ascending series of 5-s duration stimuli at 25-s intervals, beginning at 0.50 kg/cm² and increasing in 0.50 kg/cm² intervals up to tolerance or a maximum of 10 kg/cm². Pain intensity will be rated after each stimulus on a 0 (no pain) – 100 (extreme pain) numerical rating scale (NRS). Pressure pain threshold and tolerance will be determined from this procedure, as well as the PAIN50, the pressure intensity that provokes a response halfway between threshold and tolerance.

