
	Patient Global Impression of Change						SS, SS*, SS**	SS, SS*, SS**		SS, SS*, SS**
	Conner Davidson Resilience	A						SS, SS*, SS**		SS, SS*, SS**
Imaging /QST Assessments	McGill Pain Questionnaire	SS**,FBSS*, HC*								
	fMRI screening form	SS**,FBSS*, HC*								
	fMRI imaging form	SS**,FBSS*, HC*								
	QST Record Sheets	SS*,SS**, FBSS*, HC*								

A All (SS, FBSS, HC)
 SS Spine Surgery patients – Phenotyping only
 SS* Spine Surgery patients – Phenotyping + QST
 SS** Spine Surgery patients – Phenotyping + QST + imaging
 FBSS Established FBSS patients
 FBSS* Subset of FBSS getting imaging
 HC Healthy Controls
 HC* subset of HC getting imaging

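### The hypothesis linking FM score to QST is placed only in exploratory Analysis 3a, which by wording and placement uses 30 imaged surgery patients, although 50 are planned to have both measures

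*Combined protocol and SAP*

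**What the plan says.** Section II.C, Aim 3 Analyses, defines the data for Analysis 3a: "Pre-operative neuroimaging data for lumbar spine surgery patients will be split based on median baseline 2011 FM Survey Criteria score into two groups". The first of its four predictions, for patients with higher FM scores, is "more hyperalgesia and decreased pain inhibition on QST and functional magnetic resonance imaging (fMRI"). The other three concern connectivity, glutamate and gray matter volume. On numbers, the Aim 3 sample size paragraph says "We aim to recruit 30 lumbar spine surgery patients, 15 healthy controls, and 15 established-FBSS patients out of the total cohort".

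QST is planned more widely. The Overall Study Design (II.B) says of the surgery cohort that "50 will participate in phenotypic characterization and quantitative sensory testing (QST) procedures", and the QST section (II.E) says "Half of the patients (n=50) patients undergoing lumbar spine surgery will complete this testing pre-operatively". The Study Schedule after Appendix I gives the 2011 FM survey to every participant at baseline.

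Two places suggest that the imaged patients belong to the QST group. The schedule key defines SS** as "Spine Surgery patients – Phenotyping + QST + imaging", and the imaging section (II.E) begins "In addition to QST, patients enrolled in Aim 3 studies will also undergo four different neuroimaging procedures".

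Aim 2, the QST aim, carries over the Aim 1 analyses. Those are failure proportions by FM group, each construct by AOC group, a stepwise logistic model, and AOC groups against established-FBSS patients and healthy controls.

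**The concern.** The FM score is the main predictor in this study, and the Background says that the FM Survey "is hypothesized to be a surrogate measure of the degree of centralized pain". Whether the score tracks measured pain sensitivity in these surgery patients is therefore a useful question, and the plan asks it. It asks it inside an imaging analysis, where the patient count is set by scanner places and MRI eligibility (among the exclusions: BMI above 40, implanted devices, severe claustrophobia). QST apart from the scanner has no such limit.

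The plan accepts low power in Aim 3 because the neuroimaging work is investigatory. That does not explain limiting a questionnaire-to-QST comparison to the imaged patients. At stake is precision in one secondary hypothesis, which can be improved without collecting anything new.

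**Working it through.** **1. The plan's own power figures.** These cover only the Aim 1 test of failure proportions, with 50 per group and two-sided 5%. With p̄ the mean of the two rates and q = 1 − p:

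power = Φ{(|p1 − p2| − 1.96·√[2p̄(1 − p̄)/50]) / √[(p1q1 + p2q2)/50]}

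- 0.10 vs 0.50: 0.996 (plan 0.99)
- 0.15 vs 0.45: 0.918 (plan 92%)
- 0.17 vs 0.43: 0.820 (plan 82%)

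They reproduce. No power is given for FM score against QST.

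**2. Does any Aim 2 analysis relate FM score to QST?** Taking the Aim 1 analyses in turn:

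- The FM-high versus FM-low test has surgical failure as its outcome.
- The construct comparisons group patients by AOC status.
- The stepwise model could contain FM score and QST together, but as joint predictors of failure. It would not estimate how they relate to each other.
- The cross-cohort comparisons set AOC groups against established-FBSS patients or healthy controls.

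None does so.

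**3. Patients unused.** Inputs: 30 imaged (II.C) and 50 with QST (II.B, II.E). If the 30 lie within the 50, then 50 − 30 = 20 and 20/50 = 40%. With a smaller overlap, more of the 50 would fall outside the 30, so 20 is the fewest that could be unused.

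**4. Precision.** Assume an even median split: 15 vs 15, or 25 vs 25. In SD units, SE = √(2/n per group).

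- 30 patients: √(2/15) = 0.365
- 50 patients: √(2/25) = 0.283
- Ratio √(30/50) = 0.775, a fall of 22.5%

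**5. Power.** The documents give no QST effect size, so the differences below are assumptions. Two-sided 5% t-test, noncentral t with noncentrality d·√(n per group/2):

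| Assumed difference (SD) | 15 vs 15 | 25 vs 25 |
|---|---|---|
| 0.5 | 26% | 41% |
| 0.8 | 56% | 79% |
| 1.0 | 75% | 93% |

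The difference detectable with 80% power, by normal approximation (1.96 + 0.84)·√(2/n per group), is about 1.02 SD with 30 patients and 0.79 SD with 50.

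**The case against.** **The limit to 30 is not written down.** Analysis 3a gives no sample size for the QST part of item (1), and the prediction is worded about surgery patients, not imaged ones. The QST section also says that Aim 3 patients have some of the QST within their MRI protocol, so item (1) could mean scanner-linked QST only, where the restriction would be inherent. This stands as a limit on certainty. It does not remove the gap: on that reading the plan contains no FM score–QST analysis of the 50 at all.

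**Nesting is implied, not stated.** The key uses the word subset for the imaged FBSS and control groups but not for SS**, and II.B draws Aim 3 patients from the Aim 1 and 2 cohorts generally. This also stands, so the 40% is conditional.

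**Keeping FM score continuous would recover much of the power at n = 30.** This is fair. Under bivariate normality, a 0.8 SD gap between median halves corresponds to a correlation of about 0.371/0.798 = 0.465. Fisher-z power is then about 74% with 30 patients and 93% with 50. The larger sample still helps, so the two changes are separate. It would be wrong to take 0.371, the correlation with the split score, as the correlation with the continuous score.

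**The stakes are modest.** Hypothesis 3 names only neuroimaging findings, Hypotheses 2a and 2b concern QST and surgical outcome, and II.B concedes that Aim 3 may be underpowered. This stands. A reader might infer that the comparison is the study's principal test of the FM score as a surrogate. The documents give it no such role; it is one clause of an exploratory aim.

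**Conclusion.** The point holds as a cheap improvement to a secondary analysis. The FM score–QST hypothesis appears only in Analysis 3a, which by wording and placement rests on 30 imaged surgery patients, while 50 are planned to have both measures. Using all 50 reduces the standard error by 22.5%. It raises power from 26% to 41%, 56% to 79%, or 75% to 93% at assumed differences of 0.5, 0.8 or 1.0 SD. The 40% unused rests on the 30 lying within the 50; the power figures rest on an even median split, full recruitment and complete data. The primary Aim 1 test is untouched.

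A reader might go further and add the 50 established-FBSS patients to reach 100. The documents do not securely support that number. The Overall Study Design describes QST in all 50, but the schedule assigns QST record sheets only to FBSS*, the imaged subset, which is planned at 15.

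**What to change.** Take the QST part out of item (1) and add to the Aim 2 analyses: *Baseline FM score will be related to the pre-operative QST measures in all surgery patients with QST (n=50), with trapezius pressure pain threshold as the primary measure of generalized pain sensitivity and the other QST measures secondary.* The QST section already gives the trapezius threshold that role, and naming it here avoids a set of unranked tests. State whether FM score enters as a continuous variable or as a median split. Keep the fMRI part in Analysis 3a. If item (1) was meant to cover only QST done with the scan, say so and still add the Aim 2 sentence.

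Before writing any supporting model that adds established-FBSS patients, reconcile the design text with the schedule on how many of them have QST.

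The cost is one paragraph of analysis text. The surgery-patient data are already scheduled, with no added visits or procedures.
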